## RESEARCH PROTOCOL

**Brief Title: I-gel vs LMA Supreme in Laparoscopic Gynecological Surgery**

**Official Title: Comparison of I-gel and LMA Supreme Without Neuromuscular Blocker in Laparoscopic Gynecological Surgery**

### **INTRODUCTION**

Since supraglottic airway devices entered clinical practice in 1988 they have gained common popularity in anesthesia administration. Initially only entering use as an alternative to the face mask, additional new modifications have currently allowed them to enter the field of use of the endotracheal tube (ETT). A significant advantage of supraglottic airway devices is that they allow the possibility of securing the airway in cases with difficult ventilation for both tracheal intubation and mask. Additionally, the lack of neuromuscular blocker agent (NBA) requirement provides advantages leading to common use such as use in many outpatient surgical interventions and causing less stress response compared to endotracheal intubation, (1-5).

Initially the i-gel was produced in 2007 as a single-use supraglottic airway device. It includes a soft, gel-like, non-inflatable thermoelastic elastomer cuff, a flattened expanded stem and hard biting block. The biting block acts as a buccal stabilizer preventing axial rotation and sliding out of position. There is an esophagus ventilation channel allowing the passage of a gastric tube (8) (Figure 1).

The LMA-Supreme has similar characteristics to the i-gel. It has an esophagus ventilation channel allowing passage of a gastric tube and allows endotracheal intubation. Different to the i-gel it has an anatomic angle (Figures 2 and 3). The AuraGain is the only supraglottic airway device including a gastric channel, allowing endotracheal intubation and with an anatomic angle.

Many studies have found the i-gel is easily and reliably inserted, provides sufficient ventilation and is related to low morbidity rates (8). As a result during positive-pressure ventilation, it may be used as an alternative to endotracheal intubation.

### **Use of supraglottic airway devices in laparoscopic interventions**

Contrary to the commonly held view, the use of supraglottic airway devices in gynecological laparoscopy does not increase the risk of pulmonary aspiration and ventilation failure (10,11,12). SGAD's are recommended as alternatives to ETT for spontaneous respiration and positive-pressure ventilation (13,36,37). Laryngeal mask application has gained popularity for gynecological laparoscopic procedures in the United Kingdom (12,14). Additionally many previous studies have shown that LM can be successfully used to ensure appropriate pulmonary ventilation in laparoscopic surgical interventions (12,14,15). Verghese and Brimacombe did not encounter pulmonary aspiration in 1469 elective gynecology cases (16), while Malins and Cooper did not encounter it in 3000 patients (17). Bapate et al. (14) researched the incidence of regurgitation in 100 patients undergoing LM elective gynecological laparoscopy surgery. This study confirmed that the incidence of regurgitation during laparoscopy with LM was very low and supported the view that LM can be reliably used during elective laparoscopy surgery.

Miller et al. (18) compared the use of ETT, LM-P and SLIPA during laparoscopic gynecology interventions and identified advantages of LMA use. The most important of these advantages is that insertion and use of supraglottic laryngeal devices for laparoscopic surgeries does not require neuromuscular blocker agents (NBA), contrary to tracheal tube technique. Thus, for outpatient laparoscopic surgeries they indicated that supraglottic laryngeal devices may be easily inserted without requiring muscle relaxants and reduce the duration spent in the operating room compared to ETT technique. Additionally the same study stated that there was less systolic blood pressure response and later less throat pain observed compared to ETT technique (18).

Thomas et al. (19) showed that administering NBA did not change incidence of throat pain difficulty swallowing, and voice loss when a supraglottic airway device was used during positive pressure ventilation and again they reported that neuromuscular blockage did not affect success rates for LMA insertion and ease of insertion. Successful airway opening and surgical procedures have been shown to be possible without using NBA in a variety of studies (with ETT or LM) in the literature (20,21). This technique is a successful alternative when NBA are contraindicated or unwanted. In routine practice many clinics do not use NBA unless clinically indicated (22). Especially for interventions where LM is used, the use of NBA, which are not necessary for LM insertion, can be avoided. Gynecological laparoscopic interventions are appropriate for this. As a result one of the advantages of supraglottic airway device use in laparoscopic gynecological interventions may be listed as not requiring NBA. 3

Williams et al. (23) compared gynecological laparoscopic interventions in an LM group without NBA and an ETT group with NBA. The CO2 insufflation volumes and pneumoperitoneum formation durations in both groups were similar. The researchers emphasized that due to the advantages, total anesthesia/surgery duration in the LM group without NBA was shorter and this was the main output of the study.

However in our literature search, we did not encounter any clinical study comparing the i-gel and LMS for laparoscopic interventions without NBA. There is a cadaver study comparing anatomic position and performance of i-gel, Ambu AuroGain and Laryngeal mask airway Supreme (LMA-Supreme) insertion. This study found that insertion of the Ambu AuroGain required manoeuvres, however the airway leak pressure was similar to other LMA-Supreme, and the nasogastric tube transfer was similar to LMA-Supreme (38).

There are studies comparing a variety of supraglottic airway devices with each other for laparoscopic gynecological surgeries. However, in all these studies neuromuscular blocker agents were used.

Many anesthetists choose not to use neuromuscular blocker agents unless necessary for surgical procedures in routine application. As the clinical view is generally based on personal experience, the use of both neuromuscular agents and the dose management of these agents may vary between clinicians. As a result making any specific recommendation is difficult. Chassard et al. evaluated 50 patients undergoing laparoscopic gynecological surgery with TIVA anesthesia management. In this study patients were divided into 2 groups as those given neuromuscular blocker agent (atracurium) and those not given it. In terms of operation conditions, an evaluation by surgeons found no difference between the two groups (32). The use of neuromuscular blockers in gynecological laparoscopy was found not to affect the majority of hemodynamic and respiratory changes due to pneumoperitoneum or operation conditions (33, 34).

Chen et al. (35) in a broad-series laparoscopic gynecological study (n=120) used ProSeal™ as SGAD and administered neuromuscular blocker agents to half of patients (rocuronium). The results of this study showed that both ventilation and surgical conditions were the same in both groups. The authors additionally noted that the use of neuromuscular blockers in laparoscopic gynecological surgeries was not beneficial as they did not reduce the operation and recovery times. In this study they emphasized the important point of easy insertion of laryngeal mask without neuromuscular blockers. Another study questioning the use of neuromuscular blockers in laparoscopic gynecological surgeries was completed by Swann et al. This study administered inhalation anesthesia for maintenance. The patients were divided into 2 groups. While spontaneous respiration and ventilation were ensured together without using neuromuscular blocker agents in the group with laryngeal mask inserted, controlled ventilation was

applied to the group with endotracheal intubation administered atracurium. There was no significant difference found between the groups in terms of intraoperative conditions; however a limitation of this study is the very short mean surgical duration (average < 15 min).

Williams et al. (23) compared an LM group without NBA and an ETT group with NBA for gynecological laparoscopic interventions. The CO2 insufflation volumes and pneumoperitoneum formation durations were similar in both groups. The researchers emphasized that the main outcome of the study was the shorter total anesthesia/surgical duration in the LM group due to the advantage of not using NBA.

However, there are some special situations where the use of neuromuscular blockers is definitely required for laparoscopic surgeries. Routine abdominal laparoscopy anesthesia is one of these special cases. In robotic surgeries extreme or deep neuromuscular blockage improves operation conditions and patient results (30).

In our literature scan of studies researching the oropharyngeal leak pressures, ventilation parameters and especially mean airway pressure values in anesthesia for laparoscopic gynecological surgery including lower pelvic region without the use of neuromuscular blocker agents, we did not encounter a study comparing i-gel with LMA-Supreme.

## **AIM**

To compare the effects of i-gel and LMA-Supreme on ventilation parameters and surgical view during laparoscopic gynecological surgery in cases administered positive pressure ventilation without the use of neuromuscular agents.

## **MATERIAL AND METHOD**

This study will be completed after receiving permission from "Dokuz Eylül University Faculty of Medicine Clinical Research Ethics Committee" and "Medical Device Study and Authorization Coordination Department", (Protocol No: 266-SBKAEK) with informed patient consent, as a prospective, randomized and double-blind study of 102 patients in ASA classification group I-II, aged from 18 to 65 years undergoing elective laparoscopic gynecological surgery.

Patients will be divided as

Group 1 => i-gel (51 patients) (control group)

Group 2 => LMA-Supreme (51 patients) (experiment group).

Patients and surgeons performing the operations will not be aware of the airway device used. Patients in the groups will be determined with the block randomization method. By looking at a simple random number table, 102 individuals will be divided into 2 groups of 51 by using 6 blocks of groups containing.

Before anesthesia induction patients taken to the operating room will have standard monitoring applied (non-invasive blood pressure measurements, electrocardiogram, peripheral oxygen saturation measurements). For preoperative sedation 0.02 mg/kg midazolam IV will be administered. Patients will be preoxygenized for 3 minutes with 6 L/min oxygen through a face mask. For anesthesia induction after 2 minutes of 0.2  $\mu$ kg/min remifentanil and 6 mg kg propofol infusion, IV 1-2 mg kg propofol will be administered. After induction patients will be ventilated with a face mask with 6 L/min 100% oxygen.

All patients will have bispectral index monitoring (BIS, ASPECT A-2000 BIS XP monitor) to standardize anesthesia depth. BIS values will be held between 40-60. BIS values will be kept within this interval by increasing or decreasing propofol infusion by 1 mg/kg after additional bolus dose of propofol (1 mg/kg).

Airway device insertion will be performed by two researchers with more than 5 years experience.

During airway device insertion, if necessary depending on patient reaction additional doses of 0.5 mg/kg propofol will be administered.

Anesthesia maintenance will be ensured by 50% O2/air with 0.1-0.4  $\mu$  kg/min remifentanil and 50-150  $\mu$  kg/ min (4-10 mg/kg/hr) propofol IV infusion (29).

Before inserting the LMA-Supreme and i-gel, water-based K-YTM (*Johnson & Johnson Ltd. Maidenhead, UK*) gel, not containing local anesthetic material, will be spread on surfaces that will come in contact with the palate. Depending on body weight of patients LMA-Supreme numbered as follows will be inserted:

for < 50 kg: 3

50-70 kg: 4 6

70-100 kg: 5

Again depending on body weight of patients, i-gel numbered as follows will be inserted:

30-60 kg: 3

50-90 kg: 4

>90 kg: 5.

Successful insertion of LMA-Supreme or i-gel will be confirmed by square-shaped waves on capnogram, easy ventilation with respiration balloon and observation of chest movements. After confirming successful emplacement of airway device with fiberoptics, later to prevent observation of the device it will be covered. Laryngeal view will be assessed with points from 1 to 3 by the anesthesiologist (complete vocal cords view, non-obstructing epiglottis view and obstructed view).

**For successful insertion** duration (time from mouth-opening to first successful ventilation), number of attempts and ease of insertion will be recorded. Ease of insertion will be assessed as easy, difficult or unsuccessful (alternative airway management) by the anesthetist securing the airway (6,30).

In situations with 3 unsuccessful attempts at securing the airway, patients without LMA-Supreme or i-gel insertion will have airway management ensured with endotracheal intubation. **For oropharyngeal leak test** after shutting the expirium valve, air will be closed and O2 flow reduced to 3 L/min and the first pressure value when a leak sound is heard from the mouth will be recorded as oropharyngeal leak pressure. To prevent exposure of lungs to barotrauma, when peak inspiratory pressure (*peak*) of 40 cmH2O is reached the expiratory valve will be opened and the test ended (30). This test will be performed before peritoneal insufflation, 10 minutes later and immediately before desufflation and will be completed by a researcher blind to the type of airway device.

We considered the concept “margin on oropharyngeal leak pressure (OLP)” (MOLP), defined as the value for the margin of pressure between the highest PAW-pk during pneumoperitoneum and the maximum safety’s seal pressure value (SP). Our purpose is try to assess the “safety gap” on our patient’s airway (in terms of pressure) until it reaches the maximum PAW-pk permitted value under safety conditions (SP) (37).

Positive pressure respiration using a ring system will begin with 2-4 L/min fresh gas flow and FiO2 0.5 volume control with 6-8 ml/kg tidal volume and 10 respirations/min frequency.

PEEP will not be applied and I:E ratio will be 1:1,5. ETCO2 will be held from 35-45 mmHg, if necessary first respiration frequency will be increased, later tidal volume will be increased. For laparoscopic intervention, permission will be given for CO2 insufflation for peritoneal interior pressure of 15 mmHg.

Two minutes after insertion of LMA-Supreme or i-gel, before insufflation, 10 minutes after insufflation and trendelenburg position, immediately before peritoneal desufflation and before removing the airway device, ventilation parameters will be assessed.

**Respiratory Measurements recorded:** Tidal volume (TV), respiration rate (RR), peripheral oxygen saturation (SPO2), end-tidal carbon dioxide pressure (PETCO2), peak airway pressure (Ppeak), mean airway pressure (Pmean) and expiratory volume per minute (VE).

**Hemodynamic Measurements recorded:** (Simultaneous to the above measurements and additionally before induction) systolic arterial pressure (SAP), diastolic arterial pressure (DAP), mean arterial pressure (MAP), and heart rate (HR).

**Evaluation related to stomach probe:** Immediately after the airway device is inserted, through the LMA-Supreme (14F for size 3 and 16F for sizes 4 and 5) and i-gel drainage tube a 12F orogastric tube will be advanced to the stomach and stomach contents aspirated. The ease of insertion of stomach probe and amount of aspirated fluid will be recorded. Ease of insertion of orogastric tube will be classified as very easy, easy, difficult or very difficult by the administrator (9). Gastric aspiration will be 200 cmH2O during 10 seconds by a suction; (connecting it later to a collection bag).

The number of interventions of verres needle, initial intra-abdominal pressure, time for intra-abdominal pressure to reach 15 mmHg, and volume of insufflated CO2 will be recorded. Sufficiency of pneumoperitoneum during operation (sufficient/insufficient), and quality of surgical view will be assessed with points from 1 to 4 by the surgeon blind to the airway device (24).

Stomach distension will be assessed on a scale of 0 to 10 (0= empty stomach, 10= distension obstructing view of the surgical field) by a surgeon blind to the airway device immediately after insertion of the laparoscope into the abdomen and immediately before the end of peritoneal insufflation and the difference between the scores at the start and end of surgery will be recorded (15). Operation table positioning (Trendelenburg) will be limited to a maximum 30°.

When the patient is cooperative, the LMA-Supreme or i-gel will be removed and total anesthesia duration and peritoneal insufflation duration will be recorded. Complications that may develop during airway device removal (cough, vomiting, laryngeal stridor, laryngeal spasm or airway intervention requirements) will be recorded.

After removing the SGAD, the presence of blood will be assessed as:

- 1: no blood
- 2: trace amounts of blood
- 3: clear amounts of blood

Conscious patients will be taken to the recovery unit and a blind researcher will evaluate throat pain, voice loss and difficulty swallowing in the 1st and 24th hours. For evaluation of throat pain, VAS-10 (visual analog scale) will be used.

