## Statistical Analysis

In a study that was conducted by Seet et al., power was calculated as 90% as a result of the power analysis that was made for laryngeal mask airway  $OLP = >21 +/- 5 \text{ cmH}_2\text{O}$  average values; and the number of the case was determined to be 40 for each group (30).

The data have been evaluated with the SPSS (Statistical Package for Social Sciences) 15.0 package program. The fitness of the variables to normal distribution was tested with the Kolmogorov Smirnov Test. The t-test was used to compare the two groups that fit normal distribution; and the Mann Whitney U-Test was used for those that did not fit normal distribution. The variables that were defined with numbers were evaluated with the Chi-Square Test and with the Fisher's Exact Test when needed; and the significance level was taken as  $p < 0.05$ . The mean, standard deviation, median, min. and max. values of the continuous variables and their sub-groups were presented; and the frequency numbers and percentages of the class variables were presented.

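### Two researchers insert every device, but the plan neither fixes the inserter before allocation is known nor includes inserter in the analysis of insertion time, attempts and ease

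*Combined protocol and SAP*

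**What the plan says.** All four elements below are in the combined protocol and SAP.

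- **Who inserts** (MATERIAL AND METHOD): "Airway device insertion will be performed by two researchers with more than 5 years experience". No rule assigns the two researchers to patients.
- **What is measured** (MATERIAL AND METHOD, successful insertion): "duration (time from mouth-opening to first successful ventilation), number of attempts and ease of insertion will be recorded". On ease, the text is explicit about the rater: "Ease of insertion will be assessed as easy, difficult or unsuccessful (alternative airway management) by the anesthetist securing the airway". No recorder is named for duration or attempts.
- **Allocation and blinding** (MATERIAL AND METHOD): "Patients in the groups will be determined with the block randomization method", and "102 individuals will be divided into 2 groups of 51". No stratification by inserter is described, and nothing places the choice of inserter before or after the allocation is opened. On masking: "Patients and surgeons performing the operations will not be aware of the airway device used". The inserter is not listed and cannot be blind to the device being placed.
- **Analysis** (Statistical Analysis): for continuous variables, "The t-test was used to compare the two groups that fit normal distribution", with the Mann-Whitney U-test otherwise. Categorical variables are "evaluated with the Chi-Square Test and with the Fisher's Exact Test when needed". There is no inserter term and no stratified test.

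**The concern.** Insertion time, number of attempts and ease all measure a manual act, so the person performing it is an obvious candidate determinant of the result. With only two inserters, one binary covariate captures the whole of that source of variation, and the plan leaves it out.

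Two consequences need to be kept apart. The first is precision: any difference between the inserters goes into the residual variance and makes a true device difference harder to detect. The second is bias: if one inserter tends to place one device, part of the difference between inserters is credited to the device. The first follows whenever the inserters differ. The second needs a link between inserter and device.

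**Working it through.** **Inputs from the documents.** Two inserters; 51 patients per arm; significance level 0.05 (sidedness not stated, taken as two-sided); unadjusted two-group tests.

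**Inputs assumed, because the documents give none.** A gap between inserters of k = 0.3 to 1.0 within-inserter SD (0.25 to 1.0 in the simulation); a device effect of 0.5 SD; an approximately normal outcome, such as log insertion time.

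**The plan's own figure.** The only sample-size figure is 40 per group for oropharyngeal leak pressure. It cannot be reproduced because no difference to detect is given, and it has no bearing on this point. The plan states no figure for the insertion outcomes.

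**Step 1: precision when inserter is unrelated to device.** If each inserter treats about half the patients, omitting inserter inflates the outcome SD from 1 to sqrt(1 + k²/4). The noncentrality of the t-test is 0.5 / (SD × sqrt(2/51)), with sqrt(2/51) = 0.198. With inserter in the model the SD is 1, the noncentrality is 0.5/0.198 = 2.52 and power is about 70.6%.

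| Gap k (SD) | SD without inserter | Noncentrality | Power, unadjusted | Loss against 70.6% |
|---|---|---|---|---|
| 0.3 | 1.011 | 2.50 | 69.6% | 1.0 points |
| 0.5 | 1.031 | 2.45 | 67.9% | 2.7 points |
| 0.8 | 1.077 | 2.34 | 64.1% | 6.5 points |
| 1.0 | 1.118 | 2.26 | 60.9% | 9.7 points |

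**Step 2: false positives when inserter is unrelated to device.** In a simulation with no device effect (20,000 runs per setting, k = 0.25, 0.5 and 1.0) and each inserter equally likely in both arms, the unadjusted t-test rejects in 5.0% to 5.3% of runs. It holds its level.

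**Step 3: how uneven chance alone makes the arms.** The difference between arms in one inserter's share has SD sqrt(2 × 0.25/51) = 0.099, or 9.9 percentage points, so 95% of trials fall within 1.96 × 9.9 = about ±19 points. By the normal approximation:

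- A difference of at least 20 points (60/40 against 40/60) is 20/9.9 = 2.02 SD and occurs in about 4% of trials.
- A difference of at least 40 points (70/30 against 30/70) is 40/9.9 = 4.04 SD and occurs in about 0.005% of trials.

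**Step 4: what happens if inserter does follow device.** The spurious device effect is k times the difference in shares. At 70/30 against 30/70 with k = 0.5 it is 0.5 × 0.4 = 0.2 SD. The unadjusted false-positive rate at that split is 7.9%, 16.9% and 44.5% for k = 0.25, 0.5 and 1.0. With inserter in the model it stays between 4.6% and 5.2% across all splits simulated. Step 3 shows that such a split is not a chance event, so these rates describe systematic matching of inserter to device.

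**Scope of the check.** These results are for a normal outcome. No gain has been calculated for number of attempts (a small count, capped by the three-attempt rule) or for ease (three categories).

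**The case against.** The strongest case against runs as follows. Comparing randomised arms without covariates is valid, so adjusting for operator is optional efficiency. Both inserters have more than five years' experience, which points to a small gap, and at 0.3 SD the gain is one power point. The AIM section names ventilation parameters and surgical view, and the sample size rests on leak pressure. Leak pressure is measured by a blinded researcher and surgical view is scored by a blinded surgeon, so the main results are not affected.

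Most of this stands. The unadjusted tests are valid when inserter is unrelated to device, the gain at small gaps is small, and only secondary outcomes are concerned. The experience argument is weaker, because experience is not stated per device and does not establish equal skill with both.

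A reader might infer that the device comparison is already confounded by operator, with false-positive rates of the size in Step 4. The documents do not support that. No section says that inserters choose cases, prefer a device or learn the allocation before it is decided who inserts. The text is silent on the matter, and silence leaves the possibility open without showing that it happens.

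A reader might also infer that the inserters grade all their own results. Self-grading is documented for ease only.

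**Conclusion.** The point holds as a modest one. The plan omits a simple covariate that could sharpen the insertion comparisons, and it leaves open a route to bias that one sentence would close. The precision cost is about 1 to 3 power points at a gap of 0.3 to 0.5 SD and up to about 10 at 1.0 SD. It rests on an assumed device effect of 0.5 SD, an assumed gap, an approximately normal outcome and an even spread of inserters. Bias is conditional on the choice of inserter following the device, which the documents neither state nor rule out.

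The inserter's unblinded grading of ease is a separate weakness. An inserter covariate would not remove it.

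**What to change.** In MATERIAL AND METHOD, add that the inserter for each case is named before the allocation is opened, and that an inserter code is recorded on the case form.

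In Statistical Analysis, for the insertion outcomes only:

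- analyse log insertion time with a linear model containing arm and inserter;
- compare number of attempts with a Mann-Whitney test stratified by inserter;
- compare ease with a Cochran-Mantel-Haenszel test stratified by inserter;
- report the number of insertions by inserter and arm.

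State as a limitation that ease is graded by an inserter who knows the device.

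The cost is one form field, a short addition to each of the two sections and one degree of freedom, with no extra patients or staff. If data have already been collected, naming the inserter in advance is no longer possible. The adjusted analysis and the counts by arm can still be reported wherever records identify the inserter.

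### No primary outcome is named; the only powered variable, oropharyngeal leak pressure, is measured three times with no time selected and no multiplicity rule

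*Combined protocol and SAP*

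**What the plan says.** No outcome is labelled primary or main for this trial anywhere in the text provided. Four places point in different directions.

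- **Introduction, last paragraph before the Aim.** The gap in the literature is said to concern leak pressures and ventilation parameters, and mean airway pressure is singled out.
- **Aim.** This names ventilation parameters and surgical view. It does not name OLP.
- **Material and Method.** The leak test has three occasions: "This test will be performed before peritoneal insufflation, 10 minutes later and immediately before desufflation". The same section introduces a margin on OLP (MOLP), "defined as the value for the margin of pressure between the highest PAW-pk during pneumoperitoneum and the maximum" safe seal pressure. It does not say which of the three leak tests supplies that seal pressure.
- **Statistical Analysis.** The only power statement cites an earlier study and concerns OLP: "power was calculated as 90% as a result of the power analysis that was made for laryngeal mask airway" OLP of 21 ± 5 cmH2O, "and the number of the case was determined to be 40 for each group". It names no time point and no between-device difference. It is not linked to the planned enrolment, in which "102 individuals will be divided into 2 groups of 51".

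The analysis text is generic. "The t-test was used to compare the two groups that fit normal distribution", with a rank test otherwise and chi-square or Fisher tests for counts. One level covers everything ("when needed; and the significance level was taken as" p < 0.05). No variable is matched to a time, and no summary over times, repeated-measures model, testing order or adjustment is given.

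**The concern.** A single 5% level controls error only for a single identified test. Here the lead result could be OLP at any of three times, MOLP, mean airway pressure, or the outcomes in the Aim, and nothing fixes the choice in advance. If OLP is compared at each time, a difference at any one of them could be presented as the leak-pressure finding, at an error rate above 5%.

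The stated 90% power has the same difficulty. It attaches to no identified OLP time, and it does not carry over to MOLP, mean airway pressure or surgical view, for which no SD or target difference is given. A reader of the results could not tell which comparison the trial was designed to make.

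**Working it through.** **Inputs from the documents.** OLP SD 5 cmH2O (reading ± 5 as an SD), power 90%, 40 per group from the power statement, 51 per group planned, significance level 0.05, three OLP tests per patient.

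**Assumptions.** Two-sided testing, since sidedness is not stated. A common within-patient correlation ρ between OLP readings, since the documents give none; shown over a range.

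**1. The plan's own figure.** Because no between-device difference is stated, 40 per group cannot be rebuilt; only the difference it implies can be found. By the normal approximation:

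δ = SD × √(2/n) × (1.960 + 1.282) = 5 × √(2/40) × 3.242 = 3.62 cmH2O.

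The exact (noncentral t) value is 3.67. Neither number appears in the documents.

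**2. False-positive risk if OLP is tested at each time.** With independent tests it is 1 − 0.95³ = 14.3%. Readings in one patient are correlated, and the three test statistics inherit ρ. With c = 1.960:

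P(at least one) = 1 − ∫ φ(u) [Φ((c − √ρ u)/√(1−ρ)) − Φ((−c − √ρ u)/√(1−ρ))]³ du

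| ρ (assumed) | P(at least one false positive) | Simulated t-tests, 51 per arm |
|---|---|---|
| 0 | 14.3% | – |
| 0.5 | 12.5% | 12.6% |
| 0.8 | 9.8% | 9.8% |
| 0.9 | 8.4% | 8.5% |
| 0.95 | 7.3% | 7.4% |

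If correlation decays with the gap between readings (first-order autoregressive), the figures are 12.9% at 0.5 and 8.8% at 0.9, so the result does not depend on the equal-correlation pattern. One prespecified time gives 5%. Bonferroni at 0.05/3 = 0.0167 gives 4.5% at ρ = 0.5 and 3.0% at ρ = 0.9.

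**3. Price of each remedy.** Detectable difference with SD 5 and 90% power (noncentral t):

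| Per arm | Level | Detectable difference (cmH2O) |
|---|---|---|
| 51 | 0.05 | 3.24 |
| 51 | 0.0167 | 3.69 |
| 40 | 0.05 | 3.67 |

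So one named time keeps the full 51-per-arm sensitivity. Bonferroni over three times brings it back to about what 40 per arm detects at 5%. Holm is never less powerful than Bonferroni, so 3.69 is an upper limit.

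**The case against.** The strongest objection is that the 8% to 13% rests on two things that the plan does not state. OLP is never called the lead outcome, and the plan never says that it will be tested three times or that any one significant time will count as success. This stands, and the figure must be read as conditional. It shows what the described methods permit.

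A second objection is that OLP is the primary outcome in all but name: it is the only powered variable, and the Introduction mentions leak pressures when stating the gap. This has some force. But the same sentence singles out mean airway pressure, and the Aim omits OLP. Even if OLP is granted, three times remain and the power belongs to none of them.

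A third is that MOLP gives one value per patient. It is not called primary, the source of its seal pressure is open, and it has no SD or power.

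A fourth is that the timing of the second leak test is less vague than it looks. The ventilation readings in Material and Method use parallel anchors, with the middle one ten minutes after insufflation and head-down positioning. This is right, and it supplies the wording for the fix.

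Two stronger readings are not supported. A reader might take 8% to 13% as the trial's overall false-positive risk. It covers OLP only; the other variables are not quantified here. A reader might also infer from "The data have been evaluated with the SPSS" that the data had already been analysed when the plan was written. The tense allows that but does not establish it, as Material and Method is written in the future.

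**Conclusion.** The concern holds in conditional form. The absence of a designated primary outcome and OLP time in the text provided follows from reading the sections together and needs no assumption. The size does: about 8% to 13% for at least one false-positive OLP result, assuming separate two-sided 5% tests at all three times and a within-patient correlation of 0.9 to 0.5 (7.3% at 0.95; 14.3% under independence, an unlikely upper bound for repeat readings in one patient). The risk exceeds 5% throughout that range. The documents do not support saying that the plan prescribes three separate tests, or that this is the trial-wide error rate.

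This should be corrected before analysis, because neither the 5% level nor the 90% power now attaches to an identifiable result.

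**What to change.** Before any group comparison:

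- In Statistical Analysis, name OLP at the second leak test as the single primary outcome, tested once at two-sided 5%.
- Align the timing of that test with the ventilation schedule in Material and Method (ten minutes after insufflation and Trendelenburg positioning).
- Revise the Aim to name this outcome.
- Label MOLP, mean airway pressure, surgical view and all other variables secondary or exploratory, and report their between-group differences with 95% confidence intervals.

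The cost is a few sentences in Statistical Analysis and one in the Aim, with no loss of power at the named time. If claims are wanted at all three OLP times, state Holm across the three instead and accept the higher detectable difference shown above.

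If analysis had already begun, state when and how the primary outcome was chosen. That discloses the choice but does not restore a 5% error rate.
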